### **3.1.5 Treatment Beyond Progression**

Treatment beyond progression in Part 3 of this study may be allowed in select subjects with initial RECIST version 1.1 or Modified RECIST for malignant pleural mesothelioma-defined progressive disease after discussion and agreement with the BMS Medical Monitor that the benefit/risk assessment favors continued administration of study therapy (eg, subjects are continuing to experience clinical benefit as assessed by the investigator, tolerating treatment, and meeting other criteria specified in [Section 4.6](#)).

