### **3.1.7 Retreatment during Survival Follow-Up (Part 3)**

Retreatment may be allowed in Part 3 of this study with disease progression during follow-up. Subjects completing approximately 24 weeks of study therapy (or up to a maximum of 48 weeks if applicable), who enter Survival Follow-up with ongoing disease control (CR, PR, or SD) for reasons other than drug-related toxicity, may be eligible for retreatment, upon subsequent confirmed disease progression within 12 months of the last dose of study drug, on a case-by-case basis, after careful evaluation and discussion with the BMS Medical Monitor to determine whether the benefit/risk ratio supports administration of further study therapy. Subjects meeting criteria for retreatment will be treated up to an additional approximately 24 weeks with the originally assigned dose regimen (eg, same dose and dose schedule administered during the first 24 weeks) or modified dose regimen, unless that dose and schedule were subsequently found to exceed the MTD, in which case the subject will be treated at the next lower or alternate dose and schedule (see [Table 4.5.2-1](#)). Subjects entering this phase will follow the schedule as outlined in [Table 5.5.1-4](#). Samples for PK will be collected less frequently ([Table 5.5.1-4](#)).

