#### **4.6 Treatment beyond Disease Progression**

Accumulating evidence indicates a minority of subjects treated with immunotherapy may derive clinical benefit despite initial evidence of progressive disease.

Subjects treated with study drugs will be permitted to continue treatment beyond initial RECIST version 1.1-defined progressive disease, assessed by the investigator, as long as they meet the following criteria:

- Investigator-assessed clinical benefit
- Tolerance of study drug
- Stable performance status
- Treatment beyond progression will not delay an imminent intervention to prevent serious complications of disease progression (eg, central nervous system metastases).
- Subject provides written informed consent prior to receiving additional nivolumab treatment. All other elements of the main consent, including description of reasonably foreseeable risks or discomforts or other alternative treatment options, will still apply.

A radiographic assessment/scan should be performed within 6 weeks of initial investigator-assessed progression to determine whether there has been a decrease in the tumor size or continued progressive disease. The assessment of clinical benefit should be balanced by clinical judgment as to whether the subject is clinically deteriorating and unlikely to receive any benefit from continued treatment with nivolumab.

If the investigator feels that the subject continues to achieve clinical benefit by continuing treatment with the study drugs, the subject should remain on the trial and continue to receive monitoring according to the Time and Events Schedule (see [Section 5.1](#)).

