### **8.3.2.2 Efficacy**

Efficacy based on RECIST version 1.1 or Modified RECIST for malignant pleural mesothelioma (Appendix 4) will be assessed using the following secondary endpoints:

- Best overall response (BOR): defined as the best response designation over the study as a whole, recorded between the dates of first dose until the last tumor assessment prior to subsequent therapy. CR or PR determinations included in the BOR assessment must be confirmed by a second scan performed no less than 4 weeks after the criteria for response are first met. For those subjects who have surgical resection, only pre-surgical tumor assessments will be considered in the determination of BOR.
- ORR: defined as the total number of subjects whose BOR is either a CR or PR divided by the total number of subjects in the population of interest.
- Duration of response: defined as the time between the date of first response and the subsequent date of objectively documented disease progression or death, whichever occurs first. For those subjects who remain alive and have not progressed or received subsequent therapy, duration of response will be censored on the date of last tumor assessment
- PFS: defined as the time from the first dose of study medication to the date of the first objective documentation of tumor progression or death due to any cause. Subjects who did not progress nor died will be censored on the date of their last tumor assessment. Subjects who did not have any on-study tumor assessments will be censored on the date of the first dose of study medication.
- PFS rate at week 't': defined as the proportion of subjects who remain progression free and surviving at 't' weeks (eg, t=12, 24, and 36 weeks, and following the corresponding planned tumor scan visit). The proportion will be calculated by the product-limit method (Kaplan-Meier estimate) which takes into account censored data.

[figure not shown]

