## 3 TUMOR RESPONSE EVALUATION

### 3.1 Evaluation of target lesions

Complete Response (CR): **Disappearance of all target lesions.** Any pathological lymph nodes (whether target or non-target) must have reduction in short axis to < 10 mm.

Partial Response (PR): At least a **30% decrease in the sum of diameters of target lesions**, taking as reference the baseline sum diameters.

Progressive Disease (PD): At least a **20% increase in the sum of diameters of target lesions, taking as reference the *smallest sum on study*** (this includes the baseline sum if that is the smallest on study). In addition to the relative increase of 20%, the sum must also demonstrate an **absolute increase of at least 5 mm**. (*Note:* the appearance of one or more new lesions is also considered progression).

Stable Disease (SD): Neither sufficient shrinkage to qualify for PR nor sufficient increase to qualify for PD, taking as reference the smallest sum diameters while on study.

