#### **4.2 Best Overall Response: all time points**

The *best overall response* is determined once all the data for the subject is known. It is the best response recorded from the start of the study treatment until the end of treatment taking into account any requirement for confirmation. The subject's best overall response assignment will depend on the findings of both target and non-target disease and will also take into consideration the appearance of new lesions.

Best response is defined as the best response across all time points with subsequent confirmation. Complete or partial responses may be claimed only if the criteria for each are met at a subsequent time point as specified in the protocol (generally 4 weeks later).

In this circumstance, the best overall response can be interpreted as specified in Table 2. When SD is believed to be best response, it must meet the protocol specified minimum time from baseline. Measurements must have met the SD criteria at least once after study entry at a minimum interval (in general not less than 6–8 weeks) that is defined in the study protocol.

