**Table 2. Best overall response when confirmation of CR and PR *IS* required.**

Overall response	Overall response	BEST overall response
First time point	Subsequent time point	
CR	CR	CR
CR	PR	SD, PD or PR a
CR	SD	SD provided minimum criteria for SD duration met, otherwise, PD
CR	PD	SD provided minimum criteria for SD duration met, otherwise, PD
CR	NE	SD provided minimum criteria for SD duration met, otherwise NE
PR	CR	PR
PR	PR	PR
PR	SD	SD
PR	PD	SD provided minimum criteria for SD duration met, otherwise, PD
PR	NE	SD provided minimum criteria for SD duration met, otherwise NE
NE	NE	NE

CR = complete response, PR = partial response, SD = stable disease, PD = progressive disease, NE = not evaluable.

a If a CR is truly met at first time point, then any disease seen at a subsequent time point, even disease meeting PR criteria relative to baseline, makes the disease PD at that point (since disease must have reappeared after CR). Best response would depend on whether minimum duration for SD was met. However, sometimes ‘CR’ may be claimed

when subsequent scans suggest small lesions were likely still present and in fact the subject had PR, not CR at the first time point. Under these circumstances, the original CR should be changed to PR and the best response is PR.

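### Part 3 best overall response has no cut-off at first progression, so a confirmed response after progression would count in ORR (minor)

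*Protocol*

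**What the plan says.** Protocol section 8.3.2.2 defines BOR over the study as a whole, "recorded between the dates of first dose until the last tumor assessment prior to subsequent therapy". CR and PR need a confirming scan at least 4 weeks later, and scans after surgical resection are dropped. Progression is not named as a limit. ORR counts every subject whose BOR is CR or PR. SAP section 4.2.2 repeats this wording, but SAP version 1.0 describes Parts 1 and 2 only.

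Appendix 4 section 4.2 gives another window: "It is the best response recorded from the start of the study treatment until the end of treatment". It has no progression limit either.

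Section 3.1.5 states: "Treatment beyond progression in Part 3 of this study may be allowed in select subjects". Section 4.6 adds "A radiographic assessment/scan should be performed within 6 weeks of initial investigator-assessed progression" and, where the investigator still sees benefit, "the subject should remain on the trial and continue to receive monitoring according to the Time and Events Schedule". Section 3.1.7 states: "Retreatment may be allowed in Part 3 of this study with disease progression during follow-up". Table 5.1-8 schedules a baseline scan and further scans during retreatment.

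Two passages come close to a limit. Section 5.4.1 says tumor measurements are collected until progression or until the subject leaves the study. Section 4.6.1 dates progression at the initial event for analyses that use the investigator-assessed progression date.

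**The concern.** In Part 3 the same subject can be a PFS event at first progression and, some weeks later, a responder in ORR. Duration of response then has no clear end. Section 8.3.2.2 runs it from first response to a later documented progression, while section 4.6.1 puts the progression before the response began.

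Part 3B ORR is read against the historic rates and Stage 1 boundaries of Table 8.1-2. The visible text does not say how those historic rates were counted. An ORR that includes responses after progression may therefore not be comparable with them.

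**Working it through.** **Can progression be followed by PR under the text?**

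1. Appendix 4 section 3.1 measures PR as a 30% fall, "taking as reference the baseline sum diameters". Progression is a 20% rise (and at least 5 mm) from the smallest sum on study.
2. Worked case: baseline sum 100 mm, smallest sum 80 mm. Progression is met at 80 × 1.2 = 96 mm. PR is met at 100 × 0.70 = 70 mm.
3. Appendix 4 Table 1 calls the later scan PR if there is no new lesion and no non-target progression.
4. Appendix 4 Table 2, headed "Best overall response when confirmation of CR and PR" is required, lists CR, PR and NE as the first time point. It has no row for progression followed by PR.
5. Section 5.4.1 taken alone would end scans at progression, but section 4.6 and Table 5.1-8 schedule Part 3 scans after it.
6. Section 4.6.1 settles the PFS date but does not mention BOR or ORR.

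The worked case, once confirmed, has BOR = PR under section 8.3.2.2.

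**How much shrinkage is needed?** For a subject whose best result was stable disease and who progressed at exactly the 20% threshold, with the smallest sum written as a fraction of baseline:

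shrinkage = 1 − 0.70 / (1.2 × smallest sum)

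| Smallest sum / baseline | Shrinkage from progression scan |
|---|---|
| 1.00 | 41.7% |
| 0.90 | 35.2% |
| 0.80 | 27.1% |
| 0.71 | 17.8% |

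**Effect of one subject on final ORR** (Table 8.1-2 totals): 1/26 = 3.8, 1/25 = 4.0 and 1/22 = 4.5 percentage points.

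**Stage 1.** The plan's own early stopping probabilities come first, as P(X ≤ boundary) from the exact binomial at the historic ORR:

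| Cohort | n, boundary, ORR | Computed | Printed |
|---|---|---|---|
| Gastric/pancreatic | 11, 1, 0.10 | 0.697 | 0.70 |
| NSCLC | 10, 1, 0.15 | 0.544 | 0.54 |
| Ovarian | 14, 1, 0.15 | 0.357 | 0.36 |
| Mesothelioma | 12, 2, 0.20 | 0.558 | 0.45 |

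The mesothelioma row does not reproduce. That is a separate matter, and the row is not used below.

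The documents give no rate of response after progression. As an assumption, let 1, 3 or 5 percentage points of subjects respond only after progression. The chance of passing Stage 1 is 1 − P(X ≤ 1):

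| Cohort | 0 points | 1 point | 3 points | 5 points |
|---|---|---|---|---|
| Gastric/pancreatic | 0.303 | 0.345 | 0.429 | 0.508 |
| NSCLC | 0.456 | 0.492 | 0.561 | 0.624 |

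These are upper bounds, because they assume every such response is confirmed in time for the Stage 1 review. A response during retreatment would rarely be. Last dose at week 21, plus 100 days (14.3 weeks), 6 weeks to the Cycle 3 scan and 4 weeks to confirm, gives 45.3 weeks. Counting the 100 days from week 24 gives 48.3 weeks. Both are minimums, since neither allows time for the confirmed progression that must come first.

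**The case against.** The strongest reply is that section 8.3.2.2 is not ambiguous. Read alone, it gives one answer for a subject treated beyond progression: the later PR counts. A reader might infer that two analysts would reach different ORRs in this case, but the endpoint definition itself does not support that. What stands is that its one answer does not fit with the PFS date and leaves duration of response without a clear end.

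A reader might also infer that retreatment is a second, independent gap. It is not. Section 3.1.7 requires confirmed progression first, so a cut-off at first progression already covers it.

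A third tempting reading takes the chance of a cohort sitting exactly on its Stage 1 boundary at the historic ORR (0.38 gastric/pancreatic, 0.35 NSCLC, 0.25 ovarian) as the size of the problem. It is not that either. A changed decision also needs a response after progression within Stage 1.

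The different Appendix 4 window sits in general RECIST text, and section 8.3.2.2 is the trial's own definition. The two should be aligned, since a response first seen after treatment ends counts under one and not the other. That is tidying.

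Finally, some efficacy text is not visible: no section 5.4.2 appears, there are redactions, and SAP section 8 relies on company counting rules that are not shown. A rule could sit there, so its absence from the full plan cannot be asserted.

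**Conclusion.** The point holds on the visible text, as a minor one. Section 8.3.2.2, followed as written, admits a confirmed PR after progression into Part 3 ORR.

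The route is narrow. Only select subjects continue, with Medical Monitor agreement. Time points with a new lesion or non-target progression stay at progression. A subject whose best result was stable disease needs a further 18% to 42% shrinkage from a scan at the progression threshold.

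The size rests on an unknown rate. One subject is worth 3.8 to 4.5 points of cohort ORR. At an assumed 1 point, the gastric/pancreatic chance of passing Stage 1 rises by about 0.04 at most. Nothing in the documents supports 3 or 5 points over 1.

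The documents do not support a reading that the Part 3B decisions are unsound. ORR is secondary, there is no formal test, and the boundaries are guides weighed with all available data. Parts 1 and 2 are little affected, because section 3.5 ends treatment there at documented progression.

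**What to change.** In section 8.3.2.2, Appendix 4 section 4.2 and the SAP when it is extended to Part 3, state that BOR uses assessments from first dose to the earliest of first RECIST 1.1 or modified RECIST progression, subsequent therapy or surgical resection. This gives one window throughout. No counted response can then follow progression, so the question about duration of response goes too.

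List responses after progression separately, including those during retreatment, and give the baseline used for each.

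The cost is one sentence in three places and one listing, with no new data. Part 3 ORR may be slightly lower, and activity seen only after progression moves to the listing. Treatment rules and scan schedules are unchanged.

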### 5.4.1 Primary Efficacy Assessment

Tumor measurements with CT and/ or MRI, as appropriate, will be conducted at screening, at the start of Cycle 3, and then every 2 cycles ( $\pm 1$  week) during the treatment phase. Tumor measurements should be conducted earlier, if clinically indicated. Subjects with SD, PR, or CR at the last clinical follow-up visit undergo tumor assessment via CT/MRI scans every 3 to 4 months during the Survival Follow-up ([Sections 8.3.2.2](#) and [8.5](#)) phase until progression or death. Tumor measurements will be collected in all subjects until progression or the subject's

discontinuation from the study as per Table 5.1-2 to Table 5.1-8. Tumor response and progression will be evaluated in this study using RECIST version 1.1 criteria or Modified RECIST for malignant pleural mesothelioma (Appendix 4). Initial response assessment of PR or CR must be confirmed by a consecutive assessment no less than 4 weeks (28 days) later.

At the Sponsor's discretion, de-identified scans and measurements may be collected and reviewed by independent radiologists using RECIST version 1.1 criteria or Modified RECIST for malignant pleural mesothelioma at a later date or at any time during the study.

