## 8.2 Populations for Analyses

- All Enrolled Subjects: All subjects who sign an informed consent form.
- All Treated Subjects: All subjects who receive at least 1 dose of study medication.
- PK Subjects: All subjects who receive at least 1 dose of BMS-986148 and have available serum and plasma concentration data.

- Immunogenicity (ADA) Population: all treated subjects who had baseline and at least 1 post-treatment immunogenicity assessment
- ECG Evaluable Population: all treated subjects who had a baseline ECG and at least 1 on-study ECG.
- Response Evaluable Population: all treated subjects who had baseline tumor measurement and at least 1 other tumor measurement after treatment, clinical progression, or death prior to the first on-treatment tumor assessment.

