**7.5 Efficacy**

In general, efficacy analyses will be performed for All Treated Subjects unless otherwise specified. Limited efficacy analyses may be performed on the Response-evaluable Subjects (e.g., ORR summary).

Time to event distribution (e.g. progression free survival, overall survival, and duration of response) will be estimated using Kaplan-Meier (K-M) method. When appropriate, the median along with 95% CI will be provided using Brookmeyer and Crowley methodology. Available medians and confidence intervals will also be presented in K-M plots. Rates at fixed time points (e.g. PFSR at 12, 24, 36 weeks) will be derived from the K-M estimates and corresponding confidence intervals will be derived based on Greenwood formula.

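### The PFS sentence that censors subjects without a tumor assessment does not exclude deaths; it conflicts with the event definition and, applied literally, would raise PFS rates

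*Protocol*

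**What the plan says.** The PFS bullet is worded the same way in protocol 8.3.2.2 and SAP 4.2.2. It has three parts:

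1. Event: PFS is "defined as the time from the first dose of study medication to the date of the first objective documentation of tumor progression or death due". The sentence then makes clear that the cause of death does not matter.
2. General censoring: "Subjects who did not progress nor died will be censored on the date of their last tumor assessment".
3. No assessment: "Subjects who did not have any on-study tumor assessments will be censored on the date of the first dose of study medication".

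The next bullet defines the PFS rate at a given week: "The proportion will be calculated by the product-limit method (Kaplan-Meier estimate) which takes into account censored data".

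Three other places bear on the point:

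- Protocol 5.4.1 says that tumor measurements "will be conducted at screening, at the start of Cycle 3, and then every 2 cycles".
- SAP 7.5 says: "In general, efficacy analyses will be performed for All Treated Subjects unless otherwise specified".
- Protocol 8.2 admits to the Response Evaluable Population treated subjects with a baseline measurement and "at least 1 other tumor measurement after treatment, clinical progression, or death prior to the first on-treatment tumor assessment".

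**The concern.** The second sentence is limited to subjects who had neither event. The third carries no such limit. A subject who dies before any on-study scan therefore meets the first sentence (event at death) and also the third (censored at first dose), with no order of precedence between them.

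A programmer could reasonably treat the third sentence as the specific rule that overrides the general one. That programmer would be following the SAP as written, yet would be removing the earliest deaths from the analysis. Such censoring is informative, because these subjects have the worst outcome. The error can only push PFS upward. PFS is a named secondary objective and is to be reported by tumor type in expansion cohorts of about 25, where two or three reclassified deaths would be visible.

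**Working it through.** **Can the case arise?** The first planned scan is at the start of Cycle 3. That is 2 × 21 = 42 days (week 6) on the Q3W schedule and 2 × 28 = 56 days (week 8) on the QW schedule. Efficacy is analyzed in All Treated Subjects, so a death before that scan is in the PFS set. The Response Evaluable definition names this situation ("death prior to the first on-treatment tumor assessment"), so the plan foresees it.

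**Is precedence stated anywhere?** No. SAP 7.5 names the Kaplan-Meier, Brookmeyer-Crowley and Greenwood methods but adds no censoring rule. SAP section 8 refers to company-standard windowing, imputation and counting rules, whose content is not in the documents.

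**Effect of each reading.** The documents state no expected PFS rate, event count or early-death rate, so there is no planned figure to reproduce. Let n be the cohort size, m the number who die with no on-study assessment, and d = m/n. Assume no other censoring before those deaths.

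- Deaths as events: S(t) = (number event-free beyond t)/n.
- Deaths censored at day 0: the risk set starts at n - m, so the estimate is (number event-free beyond t)/(n - m) = S(t)/(1-d).

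For illustration, take n = 25 with no other loss to follow-up and these assumed event times: 6 events by week 6, 5 at week 12, 3 at week 18, 3 at week 24, 2 at week 30 and 6 at week 42. The m early deaths are among the first 6. With deaths as events, 14 of 25 are event-free beyond week 12 (56%), 11 beyond week 18 (44%) and 8 beyond week 24 (32%), whatever the value of m. The median is week 18. Under literal day-0 censoring:

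| m | d | Multiplier | 12-week rate | Week-18 value | 24-week rate |
|---|---|---|---|---|---|
| 0 | 0% | 1.00 | 14/25 = 56.0% | 11/25 = 44.0% | 8/25 = 32.0% |
| 1 | 4% | 1.04 | 14/24 = 58.3% | 11/24 = 45.8% | 8/24 = 33.3% |
| 2 | 8% | 1.09 | 14/23 = 60.9% | 11/23 = 47.8% | 8/23 = 34.8% |
| 3 | 12% | 1.14 | 14/22 = 63.6% | 11/22 = 50.0% | 8/22 = 36.4% |
| 5 | 20% | 1.25 | 14/20 = 70.0% | 11/20 = 55.0% | 8/20 = 40.0% |

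**Median.** With one or two such deaths it stays at week 18. With three, the curve is exactly 50% at week 18, so the reported median depends on the convention for a curve that touches one half. With five, it moves to week 24.

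**Scale against sampling error.** With no other censoring, the standard error of a 32% rate in 25 subjects is √(0.32 × 0.68/25) = 9.3 percentage points. The shift for one to three deaths is 1.3 to 4.4 points, so it is under half a standard error. Unlike sampling error, it always goes the same way.

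**The case against.** The strongest reply is that the bullet should be read as a whole. Death is declared an event first. The general censoring sentence then covers event-free subjects but uses the date of their last assessment, and a subject with no scan has no such date. The third sentence fills that gap, so it concerns event-free subjects only. The PFS-rate bullet fits this reading, because it counts subjects who are both alive and free of progression. The Response Evaluable definition also suggests that early deaths are meant to be counted, although it governs response, not PFS. On this reading inflation is zero. The reply is a fair one, and it rules out calling day-0 censoring of early deaths the settled rule. It does not remove the defect, because the limit appears in one sentence, is missing from the next, and has to be inferred.

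Other limits also stand:

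- The rule reaches only subjects with no on-study assessment at all. Protocol 5.4.1 allows earlier scans when clinically indicated, and the schedules in Tables 5.1-3, 5.1-5 and 5.1-7 include an assessment at end of treatment. Some subjects who die early will therefore have been scanned.
- Entry requires a life expectancy of at least 3 months and ECOG 0 to 1. This does not exclude such deaths, but nothing in the documents supports a particular rate.
- PFS is secondary and descriptive, with no formal testing.
- The company-standard rules cited in SAP section 8 might settle precedence. They cannot be seen, so they neither cure nor confirm the problem.

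**Conclusion.** The text is wrong as written. For a subject who dies with no on-study assessment, two sentences of one definition give different results in both documents, and no precedence is stated. The consequence is conditional. Applied literally, later PFS rates are multiplied by 1/(1-d), so with n = 25 and one to three such deaths a 24-week rate of 32% reads 33.3% to 36.4%. If the event definition governs, there is no effect. The death counts, the 32% rate and the absence of other early censoring are assumptions.

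A reader might go further and infer that the plan does inflate PFS, that the median must rise, or that the Stage 1 decisions are affected. The documents support none of these. The harmonised reading gives no inflation, and the illustrative median does not move with one or two deaths. The Stage 1 boundaries count responders, so the objective response rate and the Simon design do not depend on how PFS is censored.

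**What to change.** In protocol 8.3.2.2 and SAP 4.2.2, replace the third sentence with wording to this effect: *Subjects who did not die and have no on-study tumor assessment are censored at the date of first dose. A death without a prior on-study assessment is a PFS event on the date of death.*

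This follows the plan's own event definition and needs no new data. It costs one clause in each document and should be in place before database lock. It would also help to report, for each expansion cohort, how many treated subjects had no on-study assessment and how many of them died, so that readers can see how many subjects the rule touches.
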